6.4 Correlative Studies

Studies will be performed in the [name] and/or [name] laboratories (though sample processing will occur in the [name] laboratory using long-established SOPs for CLL cell isolation and storage). Biomarker assays will correlate with clinical responses. Samples will be taken at baseline/screening, during treatment and after treatment. However, not all assays will be performed for all time points for all patients, based on sample availability and leukemic cell number. Specimens will be banked in the [name] laboratory (see below).

Assays from patient plasma may include:

- Measurement of cytokine levels (including IL2, IL12, and TNF α)

Isolation of leukemic cells by Ficoll-hypaque separation and assessment, which may include:

- Assessment of signaling modulation, including the canonical Wnt pathway by multiplex qPCR (eg: Nanostring PanCancer assay)
- Measurement of phosphorylation of STAT1 by intracellular flow cytometry.
- ZAP-70, CD38, and Immunoglobulin heavy chain variable region (IgVH) mutation in CLL cells

6.4.1 Sample Collection Guidelines

Sampling Schedule

Blood sample for correlative studies will be collected at the following time points:

- Screening
- Day 1 of each cycle, pre-treatment
- Day 8 of cycle 1.
- Between 1 day and 28 days after Cycle 2, day 28
- 56 days after last DMF dose visit.

Sample Collection and Handling Instructions

Blood samples (approximately 20-30 ml as specified in the protocol) will be collected in anticoagulated (ACD) tubes. The exact time that the sample is drawn along with the exact time that the drug is administered should be recorded.

Sample Processing

Samples will be processed in the translational lab of [name], with separation of plasma, followed by isolation of mononuclear cells by Ficoll differential centrifugation.

Sample Labeling

Each tube must be labeled with the patient's study number and the date and time the sample was drawn. Data should be recorded on the Correlative Study Form, which must accompany the sample(s).

6.4.2 Specimen Banking

Patient samples collected for this study will be retained at the UCSD School of Medicine ([name] Laboratory). Specimens will be stored indefinitely or until they are used up. If future use is denied or withdrawn by the patient, best efforts will be made to stop any additional studies and to destroy the specimens. Samples will be labeled with the subject's de-identified study number and collection date. The link between study number and medical record number will be viewed over a password secured encrypted server-client.

[name], [name], and [name] will be responsible for reviewing and approving requests for research specimens from potential research collaborators outside of UCSD. Collaborators will be required to complete an agreement (a Material Transfer Agreement or recharge agreement) that states specimens will only be released for use in disclosed research. Any data obtained from the use of clinical specimens will be the property of UCSD for publication and any licensing agreement will be strictly adhered to.

The study research coordinator will review the subject's medical record for demographic and clinical information pertaining to the subject's general medical history, diagnosis, and outcomes of any treatments received. Samples and data extracted from the subject's medical record will be coded with a de-identified study number, and the subject's name and identifying information will be removed. A log that links the subject's name and identifiers to the study number will be maintained in a secure database distinct from the secure database into which the subject's clinical information will be entered

The specimens and their derivatives may have significant therapeutic or commercial value. The Informed Consent form contains this information and informs the subject that there is the potential for financial gain by UCSD, the investigator or a collaborating researcher or entity.

The following information obtained from the subject's medical record may be provided to research collaborators when specimens are made available:

- Diagnosis
- Collection time in relation to study treatment
- Clinical outcome – if available
- Demographic data

6.5 Removal of Subjects from Study Treatment and Study

Patients can be taken off the study treatment and/or study at any time at their own request, or they may be withdrawn at the discretion of the investigator for safety, behavioral or administrative reasons. The reason(s) for discontinuation will be documented and may include:

6.5.1 Patient completed study treatment;

6.5.2 Patient voluntarily withdraws from treatment (follow-up permitted);

6.5.3 Patient withdraws consent (termination of treatment and follow-up);

6.5.4 Patient is unable to comply with protocol requirements;

- 6.5.5 Patient demonstrates disease progression (unless continued treatment with study drug is deemed appropriate at the discretion of the investigator);
- 6.5.6 Patient experiences toxicity that makes continuation in the protocol unsafe;
- 6.5.7 Treating physician judges continuation on the study would not be in the patient's best interest;
- 6.5.8 Patient becomes pregnant (pregnancy to be reported along same timelines as a serious adverse event);
- 6.5.9 Development of second malignancy (except for basal cell carcinoma or squamous cell carcinoma of the skin) that requires treatment, which would interfere with this study;
- 6.5.10 Lost to follow-up.

If a research subject cannot be located to document survival after a period of 2 years the subject may be considered "lost to follow-up." All attempts to contact the subject during the two years must be documented.

7.0 Measurement of Effect

7.1 Response Criteria for Patients with Chronic Lymphocytic Leukemia

Criteria for response will utilize the IWCLL Guidelines for response, which includes clinical, hematological, and bone marrow features as outlined below (*Hallek et al.*, 2008).

Minimal Residual Disease negative: less than 0.01% CLL cell involvement by 4-color flow cytometry of bone marrow aspirate (less than 1 in 10,000 events) and meeting all other criteria for complete response.

Complete response: Requires all of the following for a period of at least two months from completion of therapy:

- Absence of significant lymphadenopathy (e.g. >1.5cm in diameter) on physical exam;
- No hepatomegaly or splenomegaly on physical exam;
- Absence of constitutional symptoms;
- Blood counts corresponding to the following values: Lymphocytes < 4,000/uL, polymorphonuclear leukocytes >1500/ μ L, platelets >100,000/ μ L, hemoglobin >11.0 g/dL (untransfused)
- Bone marrow aspirate and biopsy must be normocellular for age with <30% of nucleated cells being lymphocytes. Lymphoid nodules must be absent. If the marrow is hypocellular, a repeat determination should be performed in one month.
- The marrow should be analyzed by flow cytometry and/or immunohistochemistry to demonstrate that the marrow is free of clonal B- CLL cells.
- A CT scan or MRI documenting absence of significant lymphadenopathy should be performed if previously abnormal.
- Patients who fulfill the criteria for CR with the exception of a persistent cytopenia that is believed to be treatment related will be considered CR with incomplete bone marrow recovery (CRi). Additionally, patients who fulfill the criteria of CR with exception of having bone marrow lymphoid nodules will be considered a nodular PR.

Partial response: Requires at least 2 of the following criteria from group A, and at least one of the criteria from group B, and for a period of at least 2 months:

Group A:

- $\geq 50\%$ decrease in peripheral absolute lymphocyte count from pretreatment value, or less than 4,000/ μL .
- $\geq 50\%$ reduction in lymphadenopathy by examination or scan, or less than 1.5cm in size.
- $\geq 50\%$ reduction in splenomegaly (cm below costal margin) by examination or scan
- $\geq 50\%$ reduction hepatomegaly (total liver span) by examination or scan
- $\geq 50\%$ reduction in marrow infiltrate or B-lymphoid nodules

Group B:

- Polymorphonuclear leukocytes $\geq 1,500/\mu\text{L}$ or 50% improvement from pre-treatment value;
- Platelets $> 100,000/\mu\text{L}$ or 50% improvement from pre-treatment value;
- Hemoglobin > 11.0 g/dl (un-transfused) or 50% improvement from pre-treatment value.

Progressive Disease: Characterized by any one of the following events:

- $\geq 50\%$ increase in the products of at least two lymph nodes on two consecutive determinations two weeks apart (at least one lymph node must be ≥ 2 cm); appearance of new palpable lymph nodes.
- $\geq 50\%$ increase in the size of the liver and/or spleen as determined by measurement below the respective costal margin; appearance of palpable hepatomegaly or splenomegaly, which was not previously present.
- An increase in the number of blood lymphocytes by 50% or more with at least 5000 B lymphocytes per microliter.
- Transformation to a more aggressive histology (i.e., Richter's syndrome or prolymphocytic leukemia with $\geq 56\%$ prolymphocytes).
- *During therapy*, patients not fulfilling the above criteria for progressive disease but demonstrating a decrease in hemoglobin > 2 gm/dL, decrease $> 50\%$ in platelet or granulocyte count will not be rated as progressive disease because these may occur as both a consequence of therapy. A bone marrow biopsy in such settings is strongly encouraged.
- *After treatment*, The progression of any cytopenia (unrelated to autoimmune cytopenia), as documented by a decrease of Hb levels by more than 20 g/L (2 g/dL) or to less than 100 g/L (10 g/dL), or by a decrease of platelet counts by more than 50% or to less than $100 \times 10^9/\text{L}$ (100 000/ μL), which occurs at least 3 months after treatment, defines disease progression, if the marrow biopsy demonstrates an infiltrate of clonal CLL cells.

Stable Disease: Patients who do not fulfill the criteria for complete or partial response as defined above but do not exhibit progressive disease will be considered as having stable disease.

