1.0 BACKGROUND AND RATIONALE

1.1 Disease Background: Chronic Lymphocytic Leukemia

Chronic Lymphocytic Leukemia (CLL)/ small lymphocytic lymphoma (SLL) are a malignancies of B-cells that comprise approximately 7% of new diagnosed cases of non-Hodgkin's lymphoma. It remains the most common adult leukemia in western world, with an incidence of 3-5 per 100,000 (*Maurer and Hallek, 2013*). The National Cancer Institute estimates that 15,680 Americans were diagnosed and 4,580 died from the disease in 2013.

CLL and SLL are closely related, both manifestations of a clonal proliferation of small, mature, aberrant B-lymphocytes that are typically CD5 positive by flow cytometry or immunohistochemistry. CLL is characterized by accumulation of these leukemic cells in the peripheral blood, bone marrow, and lymphoid tissues, whereas SLL is characterized by predominance of disease in the lymph nodes and less than 5000 clonal B-cell per microliter in the peripheral blood (*Hallek et al., 2008*). CLL and SLL are managed in the same way, so CLL/SLL will be referred to simply as CLL for the remainder of this document (*Hallek et al., 2008*).

Although treatments for CLL have improved with the development of chemoimmunotherapy regimens and tyrosine kinase inhibitors, CLL remains an incurable disease. Treatment regimens that combine chemotherapy and immunotherapy (eg: Fludarabine + Cyclophosphamide + Rituximab) have produced high response rates and have been associated with an improved overall survival (*Hallek et al.*, 2010). However, patients inevitably relapse and many patients cannot tolerate chemoimmunotherapy regimens in the relapsed/refractory setting due to age, comorbidities, or compromised bone marrow function (*Brown*, 2011). Obinutuzumab (GA-101) in combination with chlorambucil was approved by the FDA in November 2013 based on efficacy as front-line therapy for patients older than 65. However, responses were not durable with this treatment either (*Goede et al.*, 2014).

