- Flushing: Commonly causes mild-to-moderate flushing (eg, warmth, redness, itching, burning sensation); flushing generally appears soon after initiation, and improves or resolves with subsequent dosing. Administration with food may decrease flushing incidence. The Canadian labeling suggests that a temporary dosage reduction or short-term (≤ 4 days) administration of aspirin (nonenteric coated) 30 minutes prior to dimethyl fumarate may also reduce the incidence and severity of flushing. Use of aspirin > 4 days has not been studied; long-term use of aspirin is not recommended.
- Gastrointestinal events: GI events (eg, nausea, vomiting, diarrhea, abdominal pain, dyspepsia) commonly occur with use; GI events generally occur in the first month of use and decrease thereafter. To improve tolerability, the Canadian labeling recommends administering with food or temporarily reducing the dosage.
- Hepatic effects: Transaminase elevations (usually <3 times ULN) were observed, generally occurring in the first 6 months of treatment.
- Lymphopenia: Decreased lymphocyte counts may occur with use. Prior to initiation, a recent CBC (within 6 months) should be reviewed to identify patients with preexisting low lymphocyte counts. Obtain CBC at least annually (or more frequently if indicated) during use. In trials, mean lymphocyte counts decreased ~30% over the first year of therapy (then stabilized), and lymphocyte counts increased (but did not return to baseline) 4 weeks following discontinuation. No difference in incidence of infection or series infections has

been observed in treated patients when compared to placebo; consider temporarily discontinuing therapy in patients with serious infections. Has not been studied in patients with preexisting low lymphocyte counts. Canadian labeling recommends treatment not be initiated in patients with signs/symptoms of a serious infection.

- Proteinuria: In clinical trials, proteinuria was reported at a slightly higher incidence than that observed with placebo; significance of these findings is unknown.

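### Under the 7.1 partial-response rule, a patient whose lymphocytes and nodes are both already below the Group A cut-offs at baseline can be scored a responder with no change on DMF

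*Combined protocol and SAP*

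**What the plan says.** Section 7.1 (Partial response) sets the count: "Requires at least 2 of the following criteria from group A, and at least one of the criteria from group B", sustained for at least two months.

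Group A has five limbs. Two carry an absolute alternative to the 50% change:
- lymphocytes: a 50% "decrease in peripheral absolute lymphocyte count from pretreatment value, or less than 4,000" per µL;
- nodes: a 50% "reduction in lymphadenopathy by examination or scan, or less than 1.5cm in size".

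The other three need a 50% fall and nothing else will do: the spleen limb ("reduction in splenomegaly (cm below costal margin) by examination or scan"), the liver limb ("reduction hepatomegaly (total liver span) by examination or scan") and the marrow limb.

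Each Group B limb can be met by an absolute value: neutrophils at or above 1,500/µL, platelets above 100,000/µL or hemoglobin above 11.0 g/dL. The alternative is a 50% improvement; the hemoglobin limb, for example, ends "un-transfused) or 50% improvement from pre-treatment value".

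Stable disease is the residual category, used only when complete response, PR and progression are all excluded. Sections 3.2.2 and 10.4 make the ORR a secondary endpoint reported with an exact 95% interval. Section 10.3 puts every patient with at least one dose in the efficacy analysis. Section 6.4 plans to relate the biomarker assays to clinical response.

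**The concern.** A response criterion should register change. Here two Group A limbs and all three Group B limbs can be met by a value that was normal before the first dose, and nothing in 7.1, 10.3 or 10.4 says such a limb does not count.

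Entry does not screen these patients out. Section 4.1 item 2 admits CLL, SLL and MBL with measurable disease, but gives no minimum lymphocyte count or node size. Item 10 accepts splenomegaly, a cytopenia or fatigue alone as the reason to treat. A patient whose disease sits mainly in the spleen can therefore enrol with low lymphocytes and no enlarged nodes.

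At stake is whether the ORR measures drug effect or, in part, baseline status. With so few patients, one misclassified case is visible in the estimate. It would also be placed with the responders when biomarkers are compared with response.

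**Working it through.** **Inputs.** The PR rule and cut-offs are from 7.1, entry limits from 4.1 (ANC above 1,000/µL, platelets at least 50,000/µL, hemoglobin at least 8.0 g/dL), the analysis population from 10.3, the exact interval from 10.4, and the sample size of 15 to 21 from 10.2. The plan gives no expected ORR, so there is no figure of its own to reproduce.

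**Step 1: apply the rule to a patient with no change.** Every percentage-change limb fails, so only the absolute alternatives can be met:

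- A = [lymphocytes < 4,000] + [nodes < 1.5 cm]
- B = [ANC ≥ 1,500] + [platelets > 100,000] + [hemoglobin > 11]
- PR if A ≥ 2 and B ≥ 1

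The values below are illustrative. All have platelets 60,000/µL and hemoglobin 8.5 g/dL, within the entry limits.

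| Unchanged patient | Lymphocytes/µL | Largest node | ANC/µL | A | B | Scored |
|---|---|---|---|---|---|---|
| (a) Nodal SLL | 3,000 | 3 cm | 1,600 | 1 | 1 | Stable |
| (b) Low-node CLL with lymphocytosis | 50,000 | 1 cm | 1,600 | 1 | 1 | Stable |
| (c) Mainly splenic disease | 3,000 | 1 cm | 1,600 | 2 | 1 | **PR** |
| (d) As (c), lower neutrophils | 3,000 | 1 cm | 1,200 | 2 | 0 | Stable |

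Only (c) is an automatic PR: both Group A cut-offs and at least one Group B threshold must be met at baseline in the same patient. Patients (a) and (b) start with one limb in hand and need one more.

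**Step 2: effect of one such patient on the ORR.** Exact (Clopper–Pearson) limits are, for 0/n, upper = 1 − 0.025^(1/n); for 1/n, lower = 1 − 0.975^(1/n) and upper = the 97.5% point of Beta(2, n − 1).

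| n | No responder | One false PR |
|---|---|---|
| 15 | 0% (0–21.8%) | 1/15 = 6.7% (0.2–31.9%) |
| 21 | 0% (0–16.1%) | 1/21 = 4.8% (0.1–23.8%) |

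**Step 3: how likely is one?** The documents give no share of patients with profile (c). Purely as an illustration, for an assumed share q the chance of at least one is 1 − (1 − q)^n. With q = 5% this is 54% at n = 15 and 66% at n = 21; with q = 10%, 79% and 89%.

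**Step 4: after the fix.** If a limb counts only when abnormal at baseline, patient (c) has one countable limb, the spleen. It has not shrunk, so A = 0 and the patient is stable.

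**The case against.** **The literal reading is uncharitable.** The node limb could mean enlarged nodes shrinking below 1.5 cm, and the lymphocyte limb a fall to below 4,000/µL. That is a sensible intent, but the text does not state it. Section 7.1 cites the iwCLL guideline and then applies it as set out in the protocol, so an assessor would work from the listed criteria. Whether the guideline itself has a baseline condition cannot be checked from these documents.

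**Other rules might catch the case.** The two-month requirement does mean that nobody is a PR on Day 1, but a value that was normal and stays normal satisfies it. Section 6.3.4.8 calls for a CT or MRI at Visit 5 when no node reaches 1.5 cm on examination, which would show non-palpable nodes. It does nothing for a patient with no enlarged nodes, and the node limb accepts examination or scan without saying which governs.

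**The profile is uncommon.** A reader might infer that any SLL or low-node patient becomes a responder. The documents do not support that: each feature supplies one of two required limbs. Section 1.1 describes SLL as mainly nodal, with "less than 5000 clonal B-cell per microliter in the peripheral blood", so a typical SLL patient would pass the lymphocyte limb and fail the node limb.

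**The drug's lymphocyte effect.** A reader might also infer that DMF's known lymphocyte lowering will generate false responses. Section 9.1 reports that "mean lymphocyte counts decreased ~30% over the first year of therapy", which is a one-year mean from earlier trials; treatment here lasts 56 days. Such a fall is a real change, and a baseline condition would still count it when it crosses 4,000/µL. It is not part of this point.

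**ORR is secondary.** This stands. It has no target or test, and 10.1.1 uses only DLTs for escalation.

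**Conclusion.** The rule is wrong as written for one specific profile: lymphocytes below 4,000/µL, nodes below 1.5 cm and at least one Group B threshold met, all at baseline. Such a patient meets the PR criteria while the disease that led to treatment is unchanged. For a patient with only one of the two Group A features, the requirement drops from two further limbs to one.

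Each false PR adds 4.8 percentage points (n = 21) to 6.7 points (n = 15) to the ORR, on the planned sample size. How many will occur is unknown. Importance is moderate: the damage is limited to a descriptive secondary endpoint and the biomarker–response comparisons. A reader might infer that dose finding is compromised, but the DLT rate and the MTD do not depend on response.

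The conclusion rests on the criteria being applied as printed in 7.1.

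**What to change.** Add to 7.1:

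1. A Group A limb counts toward PR only if that parameter was abnormal before treatment: lymphocytes at or above 4,000/µL; a node of 1.5 cm or more; an enlarged spleen; an enlarged liver; marrow only where a pretreatment marrow exists, since the Schedule of Events (6.1) has none at baseline.
2. Two such limbs must be met, or the single one if only one parameter was abnormal. Single-compartment disease is then still judged on one limb, but on the compartment that was diseased.
3. Nodes are compared by the same method, examination or scan, at baseline and at response.
4. A patient with no abnormal Group A parameter cannot be scored PR and stays in the ORR denominator as a non-responder.

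The cost is a wording change and one baseline flag per limb, from the examination and blood counts already collected at screening (6.2.6, 6.2.9) and the baseline scan in 6.2.13. No new test is needed. The reported ORR may be slightly lower. The change should be made before responses are reviewed: in an open-label single-arm trial, deciding afterwards whether such patients count would be open to bias.

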7.1.1 Progression-Free Survival

Progression-free survival (PFS) is defined as the duration of time from start of treatment until objective tumor progression or death.

7.2 Safety/tolerability

Analyses will be performed for all patients having received at least one dose of study drug. The study will use the CTCAE version 4.03 (<http://ctep.cancer.gov/reporting/ctc.html>) for reporting of non-hematologic adverse events and modified iwCLL criteria for hematologic adverse events (Appendix B).

8.0 ADVERSE EVENTS

An adverse event (AE) is any untoward medical occurrence in a patient receiving study treatment and which does not necessarily have a causal relationship with this treatment. An AE can therefore be any unfavorable and unintended sign (including an abnormal laboratory finding), symptom, or disease temporally associated with the use of an experimental intervention, whether or not related to the intervention.

8.1 Adverse Event Monitoring

Adverse event data collection and reporting, which are required as part of every clinical trial, are done to ensure the safety of subjects enrolled in the studies as well as those who will enroll in future studies using similar agents. Adverse events are reported in a routine manner at scheduled times during a trial. Additionally, certain adverse events must be reported in an expedited manner to allow for optimal monitoring of patient safety and care.

As far as possible, each adverse event should be evaluated to determine:

- duration (start and end dates)
- severity (grade)
- seriousness
- relationship to study agent
- action taken (i.e., none, study agent modification, medical intervention)
- outcome (i.e., resolved without sequelae, resolved with sequelae, ongoing)

Adverse events monitoring begins after initiation of study treatment and ends 28 days following the last administration of study treatment or study discontinuation/termination, whichever is earlier.

All patients experiencing an adverse event, regardless of its relationship to study drug (or at least possibly related to the drug), will be monitored until:

- the adverse event resolves or the symptoms or signs that constitute the adverse event return to baseline;
- any abnormal laboratory values have returned to baseline;
- there is a satisfactory explanation other than the study drug for the changes observed; or
- death.

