5.8 Duration of Therapy

In the absence of treatment delays due to adverse events, DMF will continue for 56 days as part of the clinical trial, or until:

- Disease progression
- Inter-current illness that prevents further administration of treatment
- Unacceptable adverse event(s)
- Patient decides to withdraw from the study, **OR**
- General or specific changes in the patient's condition render the patient unacceptable for further treatment in the judgment of the investigator.

Patients are not prohibited from continuing DMF through commercial source after the response assessment visit.

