6.2 Screening/Baseline Procedures

Assessments performed exclusively to determine eligibility for this study will be done only after obtaining informed consent. Assessments performed for clinical indications (not exclusively to determine study eligibility) may be used for baseline values even if the studies were done before informed consent was obtained.

All screening procedures must be performed within 30 days prior to registration unless otherwise stated. The screening procedures include:

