6.2.1 Informed Consent

6.2.2 Medical history

Complete medical, surgical and oncology history as well as history of infections are obtained at screening. Any changes from Screening (e.g. worsening severity or abnormal findings) are considered to be adverse events (AEs).

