8.6 Reporting Requirements for Adverse Events

8.6.1 Expedited Reporting

- The **Principal Investigator** must be notified within 24 hours of learning of any serious adverse events, regardless of attribution, occurring during the study or within 30 days of the last administration of the study drug.
- The **UCSD Human Research Protections Program (HRPP)** must be notified within 10 business days of “any unanticipated problems involving risk to subjects or

others” (UPR).

The following events meet the definition of UPR:

1. Any serious event (injuries, side effects, deaths or other problems), which in the opinion of the Principal Investigator was unanticipated, involved risk to subjects or others, and was possibly related to the research procedures.
 2. Any serious accidental or unintentional change to the IRB-approved protocol that alters the level of risk.
 3. Any deviation from the protocol taken without prior IRB review to eliminate apparent immediate hazard to a research subject.
 4. Any new information (e.g., publication, safety monitoring report, updated sponsor safety report), interim result or other finding that indicates an unexpected change to the risk/benefit ratio for the research.
 5. Any breach in confidentiality that may involve risk to the subject or others.
 6. Any complaint of a subject that indicates an unanticipated risk or that cannot be resolved by the Principal Investigator.
- The **FDA** will be notified within 7 calendar days of any unexpected fatal or life-threatening adverse event with possible relationship to study drug, and 15 calendar days of any event that is considered: 1) serious, 2) unexpected, and 3) at least possibly related to study participation.

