10.4 Data Analyses Plans

Primary Analysis

The rate of DLTs will be estimated along with its exact 95% confidence interval using the patients treated at the selected dose in Phase I.

Secondary analyses

The adverse events from the treatment beginning to 56 days after treatment completion or study discontinuation will be recorded for all patients. Incidence of adverse events will be summarized by event type, grade and relatedness, separately for the two dose levels.

The proportion of patients that received the selected dose and are able to complete 2 months of therapy without intolerance or disease progression will be reported. The reason for patient discontinuing treatment early will be recorded.

The objective response rate (including partial response, complete response, or nodular complete response) based on iwCLL will be estimated along with its exact 95% confidence interval.

If follow-up is available, median progression-free survival and overall survival will be estimated using the Kaplan-Meier method.

The expressions of LEF1, c-myc, Wnt pathway, STAT pathway, and STAT1 phosphorylation will be measured over time. The trajectories will be showed by graphs. We will test if the average level of these measurements throughout the treatment is significantly changed from the pre-treatment level by a paired t-test at 5% significance level. We will use the methods of Smyth (2005) to fit linear models to assess differential expression between pre- and post-treatment measurements. As we plan to conduct a large number of hypothesis tests within the gene expression outcome, we will use the Benjamini-Hochberg method to control the false discovery rate (FDR), setting it to 5%.

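### Section 8.1 stops monitoring for new adverse events 28 days after the last dose, but Section 10.4 plans their incidence to 56 days

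*Combined protocol and SAP*

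**What the plan says.** **Monitoring rule (Section 8.1).** "Adverse events monitoring begins after initiation of study treatment" and it "ends 28 days following the last administration of study treatment or study discontinuation/termination, whichever is earlier". Events that have already begun are followed until they resolve, return to baseline or are otherwise explained, or until death.

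**Analysis rule (Section 10.4).** "The adverse events from the treatment beginning to 56 days after treatment completion or study discontinuation will be recorded for all patients". The next sentence plans the table: "Incidence of adverse events will be summarized by event type, grade and relatedness, separately for the two dose levels".

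**Visits.** Section 5.1 places safety assessments 28 and 56 days after the last dose. The Schedule of Events (6.1) has a toxicity evaluation at the 56-day visit, with a window of 7 days either side. Section 6.3.5 lists an AE assessment and a concomitant-medication review at that visit (Visit 6).

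**Related rules.** Section 6.2.5 generally stops recording concomitant medication 28 days after the last dose. Section 5.8 lets patients continue DMF from a commercial source after the response visit. Section 8.6.1 requires the Principal Investigator to be told of serious events "occurring during the study or within 30 days of the last administration of the study drug". Section 6.2.2, under medical history, treats changes from Screening as AEs.

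**The concern.** Evaluation of adverse events is the first secondary objective (Section 2.0), and the incidence table in 10.4 is its main output. That table needs one rule for which new events enter the database. Staff who follow 8.1 would stop opening new AE records at day 28. Staff who follow 10.4 or the Visit 6 procedures would continue to day 56. The resulting count for post-treatment days 29 to 56 would depend on which section was read, and the table would not show it.

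Visit 6 does not settle the matter. It sends the reader to Section 9 for AE rules, but Section 9 is Agent Information. The rule itself is in 8.1, which has closed by then. Attribution is also weaker late in the window. Medication recording has generally stopped, some patients may be back on commercial drug, and the table is split by relatedness.

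**Working it through.** The plan states no figure that depends on the AE window, so there is nothing to reproduce. The check is a day count, followed by an illustration.

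**Inputs.** Planned treatment: "DMF will continue for 56 days as part of the clinical trial" (Section 5.8). Post-treatment tail: 28 days (8.1), 56 days (10.4).

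**Day count for a full course.**

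| Rule | Days from first dose |
|---|---|
| 8.1, at most | 56 + 28 = 84 |
| 10.4 | 56 + 56 = 112 |

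The difference is 112 − 84 = 28 days, namely post-treatment days 29 to 56. That is 28/56 = 50% of the post-treatment window and 28/112 = 25% of the whole window. For a patient who stops after d days the share is 28/(d + 56); at d = 28 it is 28/84 = 33%.

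The closing words of 8.1 can be read in two ways: monitoring ends at study discontinuation if that comes first, or 28 days after the earlier of last dose and discontinuation. Neither reading goes beyond 28 days after the last dose, so 84 days is a maximum under both.

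**What Visit 6 can recover.** Section 6.3.4 allows Visit 5 from 1 to 28 days after the end of cycle 2. If it takes place on day 1, the next scheduled AE assessment is Visit 6 at day 56, or days 49 to 63 with its window. Events that start and resolve in between depend on one retrospective enquiry, made when 8.1 no longer calls for new events.

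**Illustration, on an assumed constant hazard and not on trial data.** Let p be the true proportion of patients with a given event by day 112. A cut-off at day 84 shows q = 1 − (1 − p)^(84/112).

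| p | q | Relative shortfall, 1 − q/p |
|---|---|---|
| 5% | 3.8% | 24.5% |
| 20% | 15.4% | 23.0% |
| 40% | 31.8% | 20.4% |
| 60% | 49.7% | 17.2% |

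The chance that at least one of n patients has a first event only on post-treatment days 29 to 56 is 1 − (1 − (p − q))^n. At p = 20%, p − q = 0.0459. This gives 0.345 for n = 9 (the planned number at the selected dose), 0.506 for n = 15 and 0.627 for n = 21 (the planned range in total). These figures assume that 8.1 is applied strictly and that every patient completes 56 days. Early-onset toxicity would lower them.

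**The case against.** The strongest reply is that 8.1 is the outlier. Sections 5.1, 6.1, 6.3.5 and 10.4 all point to 56 days, and 10.4 is itself an instruction to record. On that view a competent site would collect to day 56 and the table would be sound. This stands in part. A reader might infer that post-treatment days 29 to 56 have no AE monitoring at all, and the documents do not support that: Visit 6 is scheduled and 8.1 follows events already under way. What remains is that the section headed as the monitoring rule says the opposite for new events, and nothing ranks one section above the other.

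Three further limits stand.

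- **Calendar days are not events.** Section 9.1 says that flushing starts soon after treatment begins and that gastrointestinal events fall mostly in the first month. A reader might take 25% as the share of events lost; the documents give no basis for that.
- **The 30-day rule is not a third AE window.** Section 8.6.1 sets a duty to notify the Principal Investigator of serious events, and it also covers the period of the study itself. It sits awkwardly with 8.1, since a serious event on day 29 or 30 is notifiable after monitoring has closed. A reporting duty need not match the collection window.
- **The start date is not a second contradiction of the same weight.** Sections 8.0, 8.1 and 10.4 all tie AEs to treatment. A reader might infer from 6.2.2 that changes between Screening and Day 1 enter the table, but that sentence can be read as naming the baseline for comparison, as 6.2.8 does.

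**Conclusion.** The conflict between 8.1 and 10.4 is real and should be reconciled. For a full course, 28 of the 112 days in the analysis window lie outside the monitoring rule for new-onset events. Those days would be captured unevenly through Visit 6 and reported as complete. The loss of events is unknown. It stays below 25% in relative terms if the hazard is constant or falling over time and treatment is completed, and it would be larger if events came late.

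A reader might also infer that the primary endpoint is compromised. The documents do not support that. Section 5.2 sets its own window for dose-limiting toxicity, from first dose to day 56, and 10.3 requires safety follow-up through that period for a patient without such a toxicity to be evaluable. The point concerns the secondary safety table only.

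**What to change.** 1. **Section 8.1:** collect AEs from first dose to 56 days after the last study dose, matching 10.4 and Visit 6. End earlier only for death, withdrawal of consent or loss to follow-up. In 10.4, anchor the 56 days to the last study dose.
2. **Section 6.2.5:** extend concomitant-medication recording to the same date. Visit 6 already includes a medication review.
3. **Commercial DMF (5.8):** record its use and flag events that occur on it, so that the table can show them separately.
4. **Section 8.6.1:** keep the 30-day rule and label it as a serious-event reporting duty, distinct from AE collection.
5. **Clarifications:** in 6.2.2, say that screening findings are the baseline and that only events new or worsened after first dose enter the 10.4 table. Correct the visit cross-references from Section 9 to Section 8.

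The alternative is to keep 28 days in 8.1 and cut the 10.4 window to 28 days, with the Visit 6 assessment then described as follow-up of ongoing events. The early-closure wording in 8.1 would still need to be made unambiguous.

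The cost is mainly protocol wording. The first route needs no new visit, but adds 28 days of AE and medication recording per patient and one item on commercial drug use.
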